12.5 Treatment Compliance

A qualified designee will be responsible for monitoring the administration of the timed oral doses of LOXO-292. A mouth check will be performed by the qualified designee to ensure that the subjects have swallowed the study drug. Once a subject has finished the dosing water, the qualified designee will use a flashlight and a tongue depressor to check the subject's mouth. Subjects' hands will also be verified to ensure that the study drug was ingested.

13 STUDY ASSESSMENTS AND PROCEDURES

The Study Events Flow Chart ([Section 6](#)) summarizes the clinical procedures to be performed at each visit. Individual clinical procedures are described in detail below. Additional evaluations/testing may be deemed necessary by the PI or designee and/or the Sponsor for reasons related to subject safety.

For this study, the blood collection for LOXO-292 is the critical parameter and needs to be collected as close to the exact time point as possible and in accordance to the time windows provided in the Study Events Flowchart ([Section 6](#)).

The Day 2 scheduled laboratory assessment must be obtained under fasting conditions (i.e., prior to the scheduled standard breakfast).

Any nonscheduled procedures required for urgent evaluation of safety concerns take precedence over all routine scheduled procedures.

13.1 Screening

Within 28 days prior to dosing, medical history and demographic data, including name, sex, age, race, ethnicity, body weight (kg), height (cm), BMI (kg/m²) and history of tobacco use will be recorded. Each subject will have a physical examination, vital sign measurements (heart rate, blood pressure, and temperature), 12-lead ECG, and the laboratory tests of serum chemistry, serology, thyroid stimulating hormone, pregnancy (females), FSH (postmenopausal females), hematology, coagulation, amylase, lipase, hemoglobin A1c, hepatic function, and urinalysis and additional tests as noted in [Section 13.2.5](#).

13.2 Safety Assessments

13.2.1 Physical Examination

Full physical examinations and abbreviated physical examinations will be performed as outlined in the Study Events Flow Chart ([Section 6](#)). An abbreviated physical examination includes, at the minimum, examination of respiratory, cardiovascular, and gastrointestinal systems, with the option for further examination of additional systems as necessary based on reported symptoms/AEs. Symptom-driven physical examinations may be performed at other times, if deemed necessary by the PI or designee.

13.2.2 Vital Signs

Single measurements of body temperature, blood pressure, and heart rate, will be measured as outlined in the Study Events Flow Chart ([Section 6](#)). Additional vital signs may be taken at any other times, if deemed necessary.

Vital sign measurements should be carried out prior to and as close as possible to having blood drawn. Blood pressure and heart rate will be measured using the same arm for each reading. Blood pressure, heart rate, and temperature measurements will be performed with subjects in a supine position (at least 5 minutes),

Blood pressure and heart rate will be measured at Screening, at Check-in (Day -1), at predose and at 2 hours (\pm 10 minutes) and 4 hours (\pm 10 minutes) postdose on Day 1, and once daily on each Study Day through EOT or ET (CRU discharge).

Body temperature will be measured at Screening, at Check-in (Day -1), at predose, and at the EOT or ET (CRU discharge).

13.2.3 ECG Monitoring

Single 12-lead ECGs will be performed as outlined in the Study Events Flow Chart ([Section 6](#)). Additional ECGs may be taken at any other times, if deemed necessary by the PI or designee.

ECGs will be performed with subjects in a supine position (at least 10 minutes). All ECG tracings will be reviewed by the PI or designee.

ECGs will be measured at Screening, at Check-in (Day -1), Days 2 and 5 postdose, and at the EOT or ET (CRU discharge). ECGs will be obtained prior to and as close as possible to the scheduled blood draws if scheduled at the same time.

13.2.4 Body Weight

Body weight (kg) will be reported as outlined in the Study Events Flow Chart ([Section 6](#)).

13.2.5 Clinical Laboratory Tests

All tests listed below will be performed as outlined in the Study Events Flow Chart ([Section 6](#)). In addition, laboratory safety tests may be performed at various unscheduled time points, if deemed necessary by the PI or designee.

Hematology

- Hemoglobin
- Hematocrit
- RBC count
- Platelet count
- RBC distribution width
- Mean corpuscular hemoglobin
- Mean corpuscular hemoglobin concentration
- Mean corpuscular volume
- WBC/leukocyte count
- WBC/leukocyte differential (absolute and percent)
- Basophils
- Eosinophils
- Lymphocytes
- Monocytes
- Neutrophils

Coagulation

- Prothrombin Time/International normalized ratio
- Activated partial thromboplastin time

Serum Chemistry*

- Blood Urea Nitrogen
- Bilirubin (total and direct)
- ALP
- AST
- ALT
- Albumin
- Calcium
- Iron
- Total Protein
- Uric Acid
- Sodium
- Potassium
- Magnesium
- Chloride
- Glucose (fasting)
- Creatine kinase
- Creatinine**
- Cholesterol (fasting)
- Triglycerides (fasting)
- Phosphorus
- Amylase
- Lipase
-

Urinalysis

- pH
- Color and appearance
- Specific gravity
- Protein***
- Glucose
- Ketones
- Bilirubin
- Blood***
- Nitrite***
- Urobilinogen
- Leukocyte esterase***

Additional Tests

- HIV ****
- HBsAg****
- HCV****
- Hemoglobin A1c ****
- Urine drug screen
 - Opiates
 - Opioids (methadone, oxycodone, and fentanyl)
 - Amphetamines
 - Barbiturates
 - Benzodiazepines
 - Cocaine metabolite
 - Methadone
 - Cannabinoids
 - Phencyclidine
- Urine cotinine
- Urine alcohol screen
- Serum pregnancy test (for females only)
- FSH (for postmenopausal females only)****
- Thyroid stimulating hormone****

- * Samples for serum chemistry will be obtained following a fast of at least 12 hours at Screening and at Check-in (Day -1); at other scheduled times, serum chemistry tests will be performed after at least an 8 hour fast. However, in case of dropouts or rechecks, subjects may not have fasted for 12 or 8 hours prior to the time that the serum chemistry sample is taken. The Day 2 scheduled laboratory assessment must be obtained under fasting conditions
- ** At Screening and Day -1, creatinine clearance will be calculated using the Cockcroft-Gault formula.
- *** If urinalysis is positive for protein, blood, nitrite and/or leukocyte esterase, a microscopic examination (for red blood cells, white blood cells, bacteria, casts, and epithelial cells) will be performed.
- **** Performed at Screening only; subjects who are positive for hepatitis B virus, HCV, or HIV by antibody will require confirmation by PCR.

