Potential effects of LOXO-292 on the central nervous system were evaluated as part of the GLP 28-day repeat-dose study in rats, in functional observational battery tests and locomotor activity assessments. Findings were limited to animals receiving the high dose on week 4 of the dosing phase, and were attributed to poor general body condition and weight changes associated with LOXO-292 administration rather than specific neurological effects. Additionally, no microscopic abnormalities in neuronal tissues were found.

In toxicology studies of LOXO-292 that were conducted in the rat and minipig, the primary pathologic findings for both species were in the tongue, pancreas, bone marrow and lymphoid tissues; while the gastrointestinal tract and ovaries were target tissues in minipig. Other target tissues identified in the rat included: multi-tissue mineralization, physeal cartilage, incisor teeth, lung, Brunner's gland, and possibly liver. Assessment of doses

associated with moribundity/death revealed a steep dose response curve for both species. LOXO-292 was not mutagenic in the GLP bacterial mutation assay. When evaluated in two in vitro assays, LOXO-292 was not genotoxic. LOXO-292 was not found to be phototoxic when evaluated in an in vitro neutral red uptake phototoxicity assay.

Based on preclinical pharmacology experiments with human cancer cells in vitro and in murine xenograft models, meaningful inhibition of RET in tumors is expected to be achievable with oral dosing regimens ≥ 40 mg/day.

Based on the nonclinical profile, including results from animal toxicology studies, theoretical risks of human exposure to LOXO-292 include the following: loss of appetite, decrease in body weight, increase in total white blood cells, neutrophils, and monocytes, decrease in albumin, increase in globulin, decreased albumin:globulin ratio, decrease in total protein, increased body temperature, lethargy, increase in cholesterol and triglycerides, increase in phosphorus, changes in taste sensation and/or development of xerostomia, gastrointestinal symptoms/signs: nausea, vomiting, loose stools, abdominal discomfort, decreases in red cell mass (red blood cell [RBC], hemoglobin, hematocrit) and reticulocytes, decrease in platelets, increases in liver function tests (alkaline phosphatase, aspartate aminotransferase, and alanine aminotransferase) and possible pancreas injury.

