12.4.1 Dose Escalation Criteria and Stopping Rules

The decision to proceed to the next higher dose administration will be made following the review of all pertinent safety/tolerability data (e.g., physical examinations, ECGs, vital signs, clinical laboratory tests, and AEs) from all subjects through a minimum of 48 hours (Day 3) postdose for Cohort 1 and through a minimum of 120 hours postdose (Day 5) for Cohort 2. Dose escalation to the next dose level (i.e., next cohort) will not take place until the PI and the Sponsor have determined that adequate safety and tolerability from the previous, lower dose, cohort has been demonstrated to permit proceeding to the next cohort.

Together they will make one of the following determinations:

1. To continue with the study as planned.
2. To continue with the study and add additional safety evaluations to subsequent cohorts.
3. In the event of the following occurrence:

One (1) or more subject(s) at a given dose level experiences a drug related CTCAE grade ≥ 3 toxicity, which is deemed clinically significant by the PI or designee with agreement from the Sponsor, a decision will be made as follows:

- Continue with the study by repeating the current dose;
- Adjust to an intermediate dose between the current dose and the next planned dose;
- Adjust to an intermediate dose between the current dose and the previous lower dose;
- Dose administration may be permitted to continue as deemed by PI, in agreement with the Sponsor, where the safety parameter assessed does not pose a subject safety risk based on safety knowledge from prior LOXO-292 studies.

4. In the event of the following occurrence:

Two (2) or more subjects in a dose level experience a drug related CTCAE grade ≥ 3 toxicity, which are deemed clinically significant by the PI or designee with agreement from the Sponsor, a decision will be made as follows:

- Dose administration may be permitted to continue as planned if deemed acceptable by PI, in agreement with the Sponsor, where the safety parameter assessed does not pose a subject safety risk based on safety knowledge from prior LOXO-292 studies;
- Evaluate an alternative dose level;
- The study may be terminated with no additional dose administration to any subjects.

5. One (1) or more subject(s) in a dose level has a drug related SAE, a decision will be made as follows:

- Evaluate an alternative dose level;

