13.4 Blood Volume Drawn for Study Assessments

Table 2: Blood Volume during the Study

Sample Type	Number of Time Points	Approximate Volume per Time Point* (mL)	Approximate Sample Volume Over Course of Study (mL)
Screening laboratory safety tests (including hematology, serum chemistry, coagulation, serology, thyroid stimulating hormone, FSH (for postmenopausal female subjects only) and serum pregnancy (for female subjects only))	1	16	16
Screening Hemoglobin A1c	1	4	4
On-study hematology, serum chemistry, and coagulation (and serum pregnancy [for female subjects only] if scheduled at same time)	4	16	64
Blood for LOXO-292 PK	21	4	84
Total Blood Volume (mL)			168*

* Represents the largest collection tube that may be used for this (a smaller tube may be used).

** If additional safety or PK analysis is necessary to obtain sufficient plasma/serum for analysis, additional blood may be obtained (up to a maximum of 50 mL).

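### A fall in reticulocytes is a listed theoretical risk, but no reticulocyte count is scheduled, and seven days of red cell measures are insensitive to it

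*Protocol*

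**What the plan says.** Protocol section 8.1.1 (Nonclinical) draws on the animal data to say that "theoretical risks of human exposure to LOXO-292 include the following". The list that follows contains "decreases in red cell mass (red blood cell [RBC], hemoglobin, hematocrit) and reticulocytes, decrease in platelets". The same section reports that in rat and minipig "the primary pathologic findings for both species were in the tongue, pancreas, bone marrow and lymphoid tissues".

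Section 13.2.5 sets the laboratory panel and states that "All tests listed below will be performed as outlined in the Study Events Flow Chart". The hematology part covers hemoglobin, hematocrit, red cell count, the red cell indices and distribution width, "Platelet count", and white cells with a full differential. Reticulocytes appear neither there nor under Additional Tests.

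Section 13.2.5 also provides that "laboratory safety tests may be performed at various unscheduled time points, if deemed necessary by the PI or designee". Section 12.4.1 includes, among the determinations open at an escalation review, "To continue with the study and add additional safety evaluations to subsequent cohorts". Neither provision mentions reticulocytes or says what would prompt a count.

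Section 8.2.3 regards the safety endpoints as sufficient to pick up any safety signal at the higher doses. Sections 12.4.1 and 14.3.1 rest the escalation review and the safety summaries on the laboratory results that are collected.

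**The concern.** The protocol identifies a possible drug effect and then omits its direct marker without giving a reason. The study takes healthy subjects above 160 mg, the highest single dose previously given to them (section 8.2.2), with a ceiling of 720 mg (section 12.1). A reduction in red cell production would have to be inferred from hemoglobin, hematocrit and red cell count over seven days after dosing. Those measures reflect the whole circulating red cell mass, which turns over slowly, and the study's own blood draws lower it as well. All subjects receive LOXO-292, so there is no untreated group for comparison.

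At stake is one safety signal, in the escalation review and in the final summaries. A later analysis plan cannot recover an analyte that was never collected.

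**Working it through.** **1. Risk list against panel.** The laboratory items in the section 8.1.1 list, matched to section 13.2.5:

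| Listed risk | In the panel? |
|---|---|
| White cells, neutrophils, monocytes | Measured |
| Red cells, hemoglobin, hematocrit | Measured |
| Platelets | Measured |
| Albumin, total protein | Measured |
| Globulin, albumin:globulin ratio | Derivable from albumin and total protein |
| Cholesterol, triglycerides, phosphorus | Measured |
| ALP, AST, ALT | Measured |
| Pancreas injury | Amylase and lipase measured |
| Reticulocytes | **Not measured, not derivable** |

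**2. When hematology is taken.** Table 2 (section 13.4) gives four on-study laboratory times. I read the flow chart (section 6) as Day -1, Day 2, Day 5 and Day 8 (EOT/ET). The minimum review before leaving Cohort 1 runs to 48 hours, so it holds only the Day 2 postdose sample. The minimum review for Cohort 2 runs to 120 hours and holds Day 2 and Day 5.

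**3. How far red cell mass can fall.** The documents give no red cell lifespan. I assume 120 days, range 100 to 130, and an even age distribution of circulating cells. Then

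fall = (share of production lost) × (days since dose) / (lifespan).

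| Time | Complete arrest, 120 days (range 130 to 100) | Half suppression, 120 days (range) |
|---|---|---|
| Day 2 (1 day) | 1/120 = 0.8% (0.8 to 1.0%) | 0.4% (0.4 to 0.5%) |
| Day 5 (4 days) | 4/120 = 3.3% (3.1 to 4.0%) | 1.7% (1.5 to 2.0%) |
| Day 8 (7 days) | 7/120 = 5.8% (5.4 to 7.0%) | 2.9% (2.7 to 3.5%) |

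At an assumed hemoglobin of 14 g/dL, the Day 8 range is 0.75 to 0.98 g/dL for complete arrest and 0.38 to 0.49 g/dL for half suppression. These are upper bounds, because they hold the suppression constant for the whole week.

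**4. How much the sampling removes.** Table 2 first: 16 + 4 + (4 × 16) + (21 × 4) = 16 + 4 + 64 + 84 = 168 mL, which reproduces the protocol's total. From Day -1 up to, but not including, the Day 8 draw there are three laboratory panels and 20 of the 21 draws in the row "Blood for LOXO-292 PK":

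3 × 16 + 20 × 4 = 48 + 80 = 128 mL.

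Blood volume is not in the documents; I assume 4 to 6 L. Then 128/6000 = 2.1% and 128/4000 = 3.2%. The Table 2 footnote says the volumes are for the largest tube that may be used, so 128 mL is a maximum for scheduled draws.

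**5. Comparison at Day 8.** Sampling (2.1 to 3.2%) is about the size of half suppression (2.7 to 3.5%). It is about half or less of complete arrest (5.4 to 7.0%).

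**6. Duration of exposure.** With the half-life of about 24 hours in section 8.1.1, the fraction remaining at 168 hours is 0.5^7 = 0.8%. Suppression lasting a full week after one dose is therefore an extreme case. A shorter or partial effect would move red cell mass by less than the table shows.

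**The case against.** The case for leaving the panel alone has several sound parts.

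- **The risk is theoretical.** It comes from a nonclinical profile that includes 28-day repeat-dose studies, whereas each subject here receives one dose. In the patient data in section 8.1.1 (153 patients, up to 240 mg twice daily), anemia is not among the events above 10%, and the one blood-count dose-limiting toxicity was thrombocytopenia, which this panel would detect. Section 8.2.2 lists no hematologic event among those attributed to LOXO-292 in healthy subjects. None of this excludes a reticulocyte effect, but it lowers the weight of the point.
- **Discretion exists.** Unscheduled tests and added evaluations are allowed. This helps only if something prompts them, and the early change at issue would not show clearly in what is scheduled. It also cannot supply a baseline count afterwards.
- **The benefit of the count is not quantified.** The documents give no variability or expected timing for reticulocytes with six subjects per cohort, and nothing shows that a count 24 hours after dosing is informative. This stands for the Cohort 1 review, to which a Day 2 count would add little.

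A reader might also infer more than the documents support:

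- *Marrow toxicity would go unseen.* It would not: platelets, white cells, neutrophils and red cell mass are all scheduled.
- *Hemoglobin is useless here.* Complete arrest for a week could move it by up to about 0.8 to 1.0 g/dL.
- *Sampling loss and drug effect are the same size.* This holds only near half suppression.
- *A fall in hemoglobin could never be attributed.* Scheduled sampling is the same in every cohort, so it would not by itself explain a dose-related trend, although six subjects per cohort give little precision.
- *The protocol contradicts itself.* Section 8.1.1 does not promise an assay for every theoretical risk. This is an unexplained gap in the panel.

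**Conclusion.** The point holds in a limited form. Reticulocytes are the single laboratory analyte in the protocol's own risk list that the panel neither measures nor allows to be derived. What goes unmeasured is the early erythroid production signal.

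The scheduled red cell measures are insensitive to that signal over seven days: at most 5.4 to 7.0% by Day 8 under complete arrest and about 3% under half suppression, with sampling alone accounting for up to 2.1 to 3.2%. These figures rest on an assumed red cell life of 100 to 130 days, an assumed blood volume of 4 to 6 L, and the maximum tube volumes in Table 2. The absence of the count from the panel rests on no assumption.

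The practical importance is modest, given a single dose and a half-life of about 24 hours. The change is still worth making because it is small and the data cannot be obtained later.

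**What to change.** Add reticulocyte count, absolute and percent, to the hematology list in section 13.2.5 at the existing on-study times (Day -1, Day 2, Day 5 and EOT/ET). Summarise it with the other laboratory data under section 14.3.1, including change from baseline, and include it in the laboratory results reviewed before escalation. It will be mainly informative at Day 5 for the Cohort 2 review and at EOT for the final safety summary. No decision threshold is proposed. If the sponsor prefers not to add the count, a sentence in section 13.2.5 should say why this listed risk is not monitored.

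The cost is a small laboratory fee for one more analyte, with no new visit or procedure. No extra blood is needed if the count can be run on the hematology tube already drawn; the documents do not state this, so it should be confirmed with the laboratory.

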13.2.6 Adverse Events

13.2.6.1 Adverse Event Definition

An AE means any untoward medical occurrence associated with the use of a drug in humans, whether or not considered drug related.

A suspected adverse reaction means any AE for which there is a reasonable possibility that the drug caused the AE. Reasonable possibility means there is evidence to suggest a causal relationship between the drug and the AE.

An AE can therefore be any unfavorable and unintended sign (including an abnormal laboratory finding), symptom, or disease temporally associated with the use of a medicinal (investigational) product, whether or not related to the medicinal (investigational) product.

13.2.6.2 Monitoring

Subjects will be monitored from Screening (signing of informed consent) until EOS (or ET if the subject discontinues and does not complete a follow up call) for adverse reactions to the study drugs and/or study procedures. At the EOT or ET visit, subjects will be asked how they

are feeling prior to check out from the CRU. During the EOS/follow-up phone call, subjects will be queried with an open-ended question such as: 'How have you been feeling since your last visit?'. AEs (whether serious or non-serious), including abnormal laboratory test value(s), abnormal vital signs, and ECG abnormalities deemed clinically significant and assessed as related to study drug by the PI or designee will be evaluated by the PI or designee and treated and/or followed through EOT or ET. AEs which are ongoing at the EOT or ET which are assessed as related to study drug by the PI (or designee) will be followed through the EOS. AEs which are ongoing at the EOS which are assessed as related to study drug by the PI or designee may be continued to be followed until the symptoms or value(s) return to normal, or acceptable levels, as judged by the PI or designee and confirmed by the Sponsor.

Treatment of SAEs will be performed by a physician, either at the CRU or at a nearby hospital emergency room. Where appropriate, medical test(s) and/or examination(s) will be performed to document resolution of event(s). Outcome may be classified as death related to AE, not recovered or not resolved, recovered or resolved, recovered or resolved with sequelae, recovering or resolving, or unknown.

13.2.6.3 Reporting

AEs and SAEs will be collected beginning at informed consent. AEs will be recorded throughout the study (i.e., from signing of the ICF until EOS or ET if the subject discontinues and does not complete a follow up call), either as subject medical history (if the event is reported as beginning prior to signing of the ICF or if the event occurs prior to study drug administration on Day 1 and is assessed as not related to study procedures by the PI [or designee]) or as AEs (if the event occurs after signing of the ICF but prior to study drug administration on Day 1 and is assessed as related to study procedures by the PI [or designee], or if the event occurs after study drug administration on Day 1 through EOT or ET regardless of relationship to study drug). From EOT or ET through EOS, only AEs assessed as related to study drug by the PI (or designee) are to be reported. All SAEs that develop from the time of ICF signing until EOS (or ET, if subject discontinues from the study and does not complete the follow up call) are to be reported.

Unless a subject withdraws consent or is withdrawn from the study and does not complete the follow up call, all subjects must be followed until the EOS. AEs which are ongoing at the EOS which are assessed as related to study drug may be continued to be followed until the symptoms or value(s) return to normal, or acceptable levels, as judged by the PI or designee and confirmed by the Sponsor. The PI (or designee) should use appropriate judgment in ordering additional tests as necessary to monitor the resolution of events. The Sponsor may request that additional safety tests be performed.

The PI or designee will review each AE and assess its relationship to drug treatment (yes [related] or no [unrelated]).

Unrelated	The time course between the administration of study drug and the occurrence or worsening of the AE rules out a causal relationship and another cause is suspected
-----------	-------------------------------------------------------------------------------------------------------------------------------------------------------------------

Related	The time course between administration of study drug and the occurrence or worsening of the AE is consistent with a causal relationship and no other cause can be identified
---------	------------------------------------------------------------------------------------------------------------------------------------------------------------------------------

Each sign, symptom, or abnormal laboratory value reported as an AE will be graded on the National Cancer Institute (NCI) Common Terminology Criteria for Adverse Events (CTCAE) version 5.0 toxicity grading scale. Only abnormal clinical laboratory results or other events deemed to be clinically significant by the PI or designee will be recorded in the database as AEs and will be graded utilizing CTCAE guidelines.

Grade refers to the severity of the AE. The CTCAE displays Grades 1 through 5 with unique clinical descriptions of severity for each AE based on the following general guideline ([NCI CTCAE 27 Nov 2017](#)):

Grade 1	Mild; asymptomatic or mild symptoms; clinical or diagnostic observations only; intervention not indicated.
Grade 2	Moderate; minimal, local or noninvasive intervention indicated; limiting age-appropriate instrumental ADL*.
Grade 3	Severe or medically significant but not immediately life threatening; hospitalization or prolongation of hospitalization indicated; disabling; limiting self-care ADL**.
Grade 4	Life-threatening consequences; urgent intervention indicated.
Grade 5	Death related to AE.

A Semi-colon indicates 'or' within the description of the grade.

Note: Not all grades are appropriate for all AEs. Therefore, some AEs are listed within the CTCAE with fewer than 5 options for grade selection. Grade 5 (death) is not appropriate for some AEs and therefore is not an option.

ADL=Activities of Daily Living

* Instrumental ADL refer to preparing meals, shopping for groceries or clothes, using the telephone, managing money, etc.

** Self care ADL refer to bathing, dressing and undressing, feeding self, using the toilet, taking medications, and not bedridden.

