- The study will be terminated with no additional dose administration to any subjects in any cohort.

Bioanalytical data may be used, if available, to guide dose-escalation decisions or for selection of an alternate dose for evaluation, and/or to confirm the sampling schedule.

A sufficient period of time will be allowed between Day 3 of Cohort 1 and the dose of the next cohort and between Day 5 of Cohort 2 and the dose of the next cohort in order for the PI and the Sponsor to adequately review the safety and tolerability data from the prior cohort.

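### The yes/no relatedness definitions in section 13.2.6.3 do not cover an adverse event with consistent timing and an identified other cause (minor)

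*Protocol*

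**What the plan says.** Section 13.2.6.3 (Reporting) asks the investigator for a yes/no judgement of relatedness on each AE and defines the two answers. Related means that the time course "is consistent with a causal relationship and no other cause can be identified". Unrelated means that it "rules out a causal relationship and another cause is suspected". There is no third category and no default.

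Section 13.2.6.1 states a different causality standard: "A suspected adverse reaction means any AE for which there is a reasonable possibility that the drug caused the AE". It explains a reasonable possibility as evidence suggesting a causal link. It does not ask that other causes be absent.

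The label is used in two places:

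- **Stopping rules (12.4.1, repeated in the Synopsis).** Rules 3 to 5 all turn on drug-related events. Rule 5 is triggered when "One (1) or more subject(s) in a dose level has a drug related SAE". It lists two actions: evaluate another dose level, or "The study will be terminated with no additional dose administration to any subjects in any cohort". Determination 1, "To continue with the study as planned", is not among them.
- **Follow-up (13.2.6.2 and 13.2.6.3).** An AE ongoing at end of treatment (EOT) must be followed to end of study (EOS) if it is assessed as related. Between EOT and EOS, a non-serious AE is reported only if it is assessed as related.

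**The concern.** Each definition joins two conditions, one on timing and one on other causes, and the second is not the mirror image of the first. Some events can therefore fail both, although the investigator must still answer yes or no. Two investigators could apply the text faithfully to the same event and answer differently.

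The event left out is an ordinary one: it follows dosing at a plausible interval, and a competing explanation has been found. Such an event may still be a suspected adverse reaction under 13.2.6.1. For a serious AE (SAE), the answer determines whether rule 5 applies. For a non-serious AE, it determines whether follow-up and reporting to EOS are mandatory. These definitions are written into the protocol itself, so this is not detail left to a later analysis plan.

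**Working it through.** **1. Cross the two conditions.** Inputs: the two definitions in 13.2.6.3.

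| Time course | Other cause | Result |
|---|---|---|
| Consistent | None suspected | Related |
| Consistent | Suspected, not identified | Related |
| Consistent | Identified | **Neither** |
| Ruled out | None suspected | Neither |
| Ruled out | Suspected, not identified | Unrelated |
| Ruled out | Identified | Unrelated |

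Two of the six cells are unclassified. In the fourth row, timing alone excludes the drug, so the practical answer is no. The third row is the only one where the answer is open. If timing could be neither consistent nor ruled out, those events would be unclassified too. Reading consistent as not ruled out removes that case, and I take that reading.

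**2. Compare with 13.2.6.1.** A third-row event fails Related because another cause was identified. It can still pass the reasonable-possibility test, which carries no such condition.

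**3. Rule 5.** The trigger is one subject in a planned cohort of 6, so a single relatedness call can decide it. If the SAE is related, the listed actions are another dose level or termination. If it is not, continuing as planned remains available, subject to the general safety review. For a third-row SAE the protocol does not say which applies. Rules 3 and 4 are less affected, because they also need a judgement of clinical significance and already permit dosing to continue.

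**4. After EOT.** EOT is at 168 hours. Half-life is about 24 hours in healthy subjects and 20 hours in patients (8.1.1).

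- 168 / 24 = 7 half-lives; 0.5^7 = 0.78% of drug remaining.
- 168 / 20 = 8.4 half-lives; 0.5^8.4 = 0.30% remaining.

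This assumes that the half-life at 320 to 720 mg is like that seen so far. Section 8.2.2 reports clearance falling with dose in patients, so the remainder could be larger. On this assumption few new drug effects would start after EOT. What remains is mainly AEs already ongoing at EOT, over the 7 - 2 = 5 to 7 + 2 = 9 days until the EOS call.

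**5. Illustration for follow-up only.** Decreased hemoglobin is a listed theoretical risk (8.1.1). From Table 2 in 13.4, using the largest tubes:

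- Check-in through EOT: 4 x 16 + 21 x 4 = 64 + 84 = 148 mL. Adding screening, 16 + 4, gives the stated total of 168 mL.
- After dosing: 3 x 16 + 20 x 4 = 48 + 80 = 128 mL.

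Assume that the investigator records a post-dose hemoglobin decrease as a clinically significant AE and identifies blood sampling as another cause. It falls in the third row, so whether follow-up past EOT is mandatory is undefined. The example is not serious and does not engage rule 5.

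**The case against.** The best case against the point has four parts.

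- **Calling an SAE unrelated does not clear escalation.** Sections 10.1 and 12.4.1 bar the next cohort until the investigator and Sponsor have reviewed all pertinent safety data and judged tolerability adequate, with no relatedness filter. Every SAE reaches the Sponsor within 24 hours whatever its label (13.2.6.4), and the Sponsor or the CRO may terminate (15.2). Rule 5 is itself loose: the other dose level need not be lower, and the Cohort 2 and 3 doses are already stated as upper limits. All of this stands and limits the size of the point.
- **Follow-up is not left unprovided.** Section 13.2.6.3 keeps subjects under observation to EOS and allows further tests. Section 10.1.1 requires results to be available before release, allows a longer stay, and provides a call to every dosed subject. This stands too. Only the mandatory status of AE follow-up and reporting is unclear.
- **Relatedness is a medical judgement, and failing Related naturally means no.** That default is plausible but unwritten. It would also place outside rule 5 an SAE that meets the protocol's own reasonable-possibility standard.
- **Section 12.4.1 does not cite 13.2.6.3.** True: applying these definitions to rule 5 is an inference. It is a sensible one, since only 13.2.6.3 defines related and unrelated. The other standard, in 13.2.6.1, is not tied to the rules either.

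**Conclusion.** The definitions are not exhaustive, and the Related test is stricter than the protocol's own causality standard. The severity is minor: there is one working gap, with bounded consequences for rule 5 and for follow-up and reporting after EOT.

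A reader might infer more than the protocol supports:

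- **That an SAE in the gap lets escalation proceed unchecked.** The general review and the power to stop do not depend on the label.
- **That the primary safety results are biased.** Post-dose AEs through EOT are recorded regardless of relationship, so incidence of treatment-emergent AEs over that period is unaffected.
- **That drug-related events will be undercounted.** The documents give no basis for the frequency or direction of misclassification.
- **That any competing explanation opens the gap.** A merely suspected cause leaves Related available; only an identified one does not.

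The conclusion rests on reading the two definitions as written and on drug-related in 12.4.1 meaning related under 13.2.6.3. The small post-EOT effect rests on the half-life assumption above.

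**What to change.** In 13.2.6.3, define Related as a reasonable possibility that the drug caused the AE, which is the 13.2.6.1 test, and Unrelated as every other AE. In 12.4.1 and the Synopsis, state that drug-related in rules 3 to 5 uses this definition.

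These are wording changes only. The downside is that somewhat more AEs may be classed as related, which is the cautious direction when escalating in healthy subjects.

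The overlap among rules 3, 4 and 5 should be raised separately. For example, a drug-related, clinically significant SAE of Grade 3 or higher meets both rule 5 and rule 3, where "Dose administration may be permitted to continue as deemed by PI, in agreement with the Sponsor". The new definition does not resolve that overlap, and it carries no weight in the severity given here.
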